5.3 Lifestyle Considerations

Abuse of alcohol, barbiturates, amphetamines or narcotics is restricted as indicated in Section 5.2. Smoking is prohibited at least 24 hours prior to the Screening GEBT and during the conduct of the study. There are no other specific lifestyle restrictions in the study.

5.3.1 Meals and Dietary Restrictions

Please refer to Section 4.1 for details regarding the standardized low calorie meal that the patients will consume at Visits 2 and 6. Please refer to the SoA (Table 1) for timing of the GEBT.

5.4 Screen Failures

Screen failures are defined as patients who consent to participate in the clinical study but are not subsequently enrolled in the study.

Version 3.0 36 of 85 20 April 2022

Individuals who do not meet certain criteria (e.g. lab values) for participation in this study (screen failure) may be rescreened. The GEBT test will not be repeated on a patient that does not meet GEBT entry criteria.

6 Study Treatment and Concomitant Therapy

Study treatment is defined as any investigational treatments, marketed product, or placebo, or intended to be administered to a study patient according to the study protocol.

6.1 Treatments Administered

Table 3 Study Treatments Administered

Study Treatment	PCS12852	Placebo
Dosage Formulation	Tablet	Tablet
Unit Dose Strengths	0.1 mg and 0.5 mg	N/A
Route of Administration	Oral	Oral

Packaging and Labeling

PCS12852 tablets and matching placebo tablets will be packaged in high density polyethylene bottles respectively.

Each patient's study medication will be packaged in a study-specific box (kit) and shipped to the study site by a central distribution site.

Treatment Schedule

Regardless of the patient's assigned treatment group, each patient will take one tablet from their assigned kit at approximately the same time each morning and at least 30 minutes prior to a meal starting on Day 1 for 28 days. For Day 28, the patients will be asked to fast overnight prior to the morning dose on Day 28 and the subsequent GEBT. The patient will be asked to document the timing of each dosing via a dosing diary.

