Patients will return to the site for Visit 3 (Randomization) where patients who meet the criteria based on having moderate to severe symptoms based on the ANMS GCSI-DD and moderate to severe delay in gastric emptying will be randomized in a 1:1:1 ratio into three treatment groups, PCS12852 0.1 mg, PCS12852 0.5 mg or placebo.

At Visit 3, patients will answer a series of assessments including the following: Patient Assessment of Gastrointestinal Disorders Symptom Severity Index (PAGI-SYM), Patient Assessment of Upper Gastrointestinal Disorders – Quality of Life (PAGI-QOL), Patient Global Impression of Severity (PGI-S) and the Patient Global Impression of Change (PGI-C). Patients will arrive fasting and have PK samples drawn prior to receiving the first dose and at the following times after the first dose: 0.5, 1, 2, 4, 6, and 8 hours. The investigator will assess the patient through the C-SSRS as well as the Clinical Global Impression- Severity scale (CGI-S) and Clinical Global Impression – Improvement scale (CGI-I).

Patients will take their assigned treatment for 28 days. During the treatment period, the patients will also complete the ANMS GCSI-DD. Each patient will be told to take one tablet from their assigned kit at approximately the same time each morning, at least 30 minutes prior to a meal (actual dosing times will be captured via a dosing diary), starting on Day 1 for 28 days. Patients will return to the clinic on Day 7 and Day 14 to be assessed in a blinded manner for safety and tolerability of the study treatment as well as have the investigator assess the patient for suicidal tendencies or ideations via the C-SSRS.

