 - g. Total bilirubin level ≥ 2 x ULN unless the individual has been diagnosed with Gilbert's disease and this is clearly documented
 - h. Estimated glomerular filtration rate < 40 mL/min/1.73 m^2 based on the Modification of Diet in Renal Disease formula
 - i. Creatinine $\geq 3 \text{ mg/dL}$
 - j. Positive human immunodeficiency virus serology
 - k. Evidence of active Hepatitis B Virus infection

Version 3.0 11 of 85 20 April 2022

Name of Investigational Product: PCS12852

Name of Active Ingredient: PCS12852

- 1. Evidence of active Hepatitis C Virus infection
- 27. Women who are pregnant or breastfeeding.
- 28. Any other medical condition, serious intercurrent illness, or extenuating circumstance that, in the opinion of the Investigator, would preclude participation in the study.
- 29. Use of any investigational product within 30 days prior to baseline or currently enrolled in another study that involves clinical intervention.
- 30. Currently taking known P-gp and BCRP inhibitors or inducers and gastric acid reducing agents. e.g., proton pump inhibitors or H2 receptor antagonists.

Investigational product, dosage and mode of administration

Group	Dosage Forms
PCS12852	0.1 mg tablet
PCS12852	0.5 mg tablet
Placebo	Matching tablet

Patients in each assigned treatment group, will take one tablet, once daily by mouth at approximately the same time each morning, and at least 30 minutes prior to a meal) during the treatment period of the study. The patient will be asked to complete a dosing diary to document actual dosing times.

Criteria for Evaluation:

Primary Endpoints

- Change in gastric emptying rate from baseline as determined by the AUC of the gastric emptying rate over time as assessed by the GEBT at Visit 6 (Day 28) after administration of the PCS12852 or placebo.
- Change in gastric emptying rate from baseline using the t₁₀ and t₅₀ metric for gastric emptying rate.
- Concentrations of PCS12852 in plasma; PK parameters will be estimated from concentration-time data using noncompartmental methods, as data permit.

Secondary Endpoints

• Change from baseline in the ANMS GCSI-DD (i.e., Day-7 to Day -1) (predose) and Day 7 (Day 1 to Day 7).

Version 3.0 12 of 85 20 April 2022

Name of Investigational Product: PCS12852

Name of Active Ingredient: PCS12852

- Change from baseline in the ANMS GCSI-DD (i.e., Day-7 to Day -1) (predose) and Day 14 (Day 8 to Day 14).

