Patients will return to the site for Day 1 (Visit 3 [Randomization]) where patients who meet the criteria for having moderate to severe symptoms based on the ANMS GCSI-DD will be randomized in a 1:1:1 ratio into three treatment groups, PCS12852 0.1 mg, PCS12852 0.5 mg or placebo. At Visit 3, patients will answer a series of questionnaires including the Patient Assessment of Gastrointestinal Disorders Symptom Severity Index (PAGI-SYM), Patient Assessment of Upper Gastrointestinal Disorders – Quality of Life (PAGI-QOL), Patient Global Impression of Severity (PGI-S) and the Patient Global Impression of Change (PGI-C). Patients will arrive in a fasted condition and have PK samples drawn prior to receiving the first dose and at the following times after the first dose, 0.5, 1, 2, 4, 6, and 8 hours. The ECG should be performed prior to the 4-hour PK draw between the 2- and 4-hour samples. The investigator will assess the patient through the C-SSRS as well as the CGI-S and CGI-I.

Patients will return to the site on Day 7 (Visit 4) and Day 14 (Visit 5) to undergo safety and tolerability assessments as per the Schedule of Assessments, along with the investigator assessing the patient for the C-SSRS to ensure the patient does not have any suicidal tendencies

Version 3.0 30 of 85 20 April 2022

or ideation. Sites will be asked to schedule the patient's visit so that the ECG can be performed approximately 4 hours after the patient's dose.

Patients will take their assigned treatment once daily for 28 days and will return to the site on Day 28 (Visit 6) for their final dose. On Visit 6, PK samples will be drawn and the GEBT will be repeated. During the treatment period, the patients will also complete the ANMS GCSI-DD. Each patient will be told to take one tablet from their assigned kit each day at approximately the same time each morning, at least 30 minutes prior to a meal (actual dosing times will be captured via a dosing diary), while fasting starting on Day 1 for 28 days.

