8.2.3 Electrocardiograms

A 12-lead ECG will be obtained as outlined in the SoA (Table 1) using an ECG machine after the patient has rested for 5 minutes in supine position. At Visit 3 (Randomization) and Visit 6 (Day 28), the ECG will be performed prior to the 4-hour PK draw. At Visit 4 and Visit 5, the ECG will be performed approximately 4 hours after the patient's dose. The Investigator will report whether the ECG is normal or abnormal and if the result is considered clinically significant or not.

All clinically significant ECG abnormalities occurring during the study should be documented as AEs. The ECG performed at Screening will be recorded as the baseline assessment. Standard ECG parameters, including heart rate, QRS, PR, QT, Bazett's correction for QT (QTcB), and Fridericia's correction for QT (QTcF) intervals will be measured. The ECGs will be overread by the Investigator to assess any abnormalities.

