10.1.8 Protocol Approval and Amendment

Before the start of the study, the study protocol and/or other relevant documents will be approved by the IEC/IRB/Competent Authorities, in accordance with local legal requirements. The Sponsor must ensure that all ethical and legal requirements have been met before the first patient is enrolled in the study.

This protocol is to be followed exactly. To alter the protocol, amendments must be written, receive approval from the appropriate personnel, and receive IRB/IEC/Competent Authority approval prior to implementation (if appropriate). In the US: Following approval, the protocol amendment(s) will be submitted to the Investigational New Drug Application under which the study is being conducted.

Administrative changes (not affecting the patient benefit/risk ratio) may be made without the need for a formal amendment. All amendments will be distributed to all protocol recipients, with appropriate instructions.

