10.2 Appendix 2: Clinical Laboratory Tests

- All clinical laboratory tests should be done after patients have fasted for at least 8 hours.
- The tests will be performed by the central laboratory, unless prior approval is received from the Sponsor.
- Protocol-specific requirements for inclusion or exclusion of patients are details in Sections 5.1 and 5.2.
- Additional tests may be performed at any time during the study as determined necessary by the Investigator or required by local regulations.
- Investigators must document their review of each laboratory safety report.

Table 6 Protocol-required Safety Laboratory Tests

Laboratory Tests	Parameters	
Hematology	Platelet count	WBC count with differential:
	RBC count	Neutrophils
	Hemoglobin	Lymphocytes
	Hematocrit	Monocytes
	RBC indices:	Eosinophils
	Mean corpuscular volume (MCV)	Basophils
	Mean corpuscular hemoglobin (MCH)	
	% Reticulocytes	
Clinical chemistry	BUN	AST/SGOT
	Potassium	Total and direct bilirubin
	Creatinine	ALT/SGPT
	Sodium	Total protein
	Glucose, fasting	Alkaline phosphatase
	Calcium	Chloride
	Phosphorus	Albumin
	Bicarbonate	

Version 3.0 66 of 85 20 April 2022

Routine urinalysis	Specific gravity pH, glucose, protein, blood, ketones, by dipstick Microscopic examination (if blood or protein is abnormal)
Pregnancy testing	Highly sensitive serum and/or urine hCG pregnancy test (as needed for women of childbearing potential) at timepoints detailed in Section 8.3.5.
Other screening tests	HbA1c and TSH will be done at Screening only Follicle-stimulating hormone and estradiol (as needed in women of non-childbearing potential only) Urine alcohol and drug screen (to include at minimum: amphetamines, barbiturates, cocaine, opiates, THC and benzodiazepines) Serology (HIV antibody, hepatitis B surface antigen (HbsAg), and HCV antibody) [HCV PCR will be done for any HCV Ab positive result] All study required laboratory assessments will be performed by a central laboratory.

NOTES:

1. Local urine testing will be standard for the protocol unless serum testing is required by local regulation or IRB/IEC.

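### Section 4.1 requires fasted daily dosing, but Section 6.1 and both Synopsis statements do not, leaving up to 26 home doses per patient without a consistent food rule

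*Combined protocol and SAP*

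**What the plan says.** Four places in the protocol set the rule for the daily tablet.

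- Section 4.1 (Overall Design) gives the 30-minute rule and adds a fasting condition: "actual dosing times will be captured via a dosing diary), while fasting starting on Day 1 for 28 days".
- Section 6.1 (Treatments Administered, Treatment Schedule) gives the 30-minute rule without that condition: "at approximately the same time each morning and at least 30 minutes prior to a meal starting on Day 1 for 28 days". It then singles out one day: "For Day 28, the patients will be asked to fast overnight prior to the morning dose on Day 28".
- The Synopsis methodology has almost the same sentence as 4.1, but without the fasting words: "actual dosing times will be captured via a dosing diary), starting on Day 1 for 28 days".
- The Synopsis paragraph on dosage and administration also leaves fasting out: "and at least 30 minutes prior to a meal) during the treatment period of the study".

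Section 5.3.1, the section on meals and dietary restrictions, deals only with the breath-test meal. Section 10.1.8 states: "This protocol is to be followed exactly".

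The dosing diary is described in the Synopsis and in Sections 4.1, 6.1 and 6.4 as a record of doses and their times. Section 6.4 adds questioning and tablet counts at visits, and a general instruction to record departures from the dosage regimen. No described record has a field for meals or fasted state.

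**The concern.** Taking a tablet 30 minutes before a meal restricts food after the dose, not before it. A mid-morning dose after breakfast and ahead of the next meal satisfies Section 6.1 and the Synopsis but breaches Section 4.1. Naming a fast for Day 28 alone also invites the reading that other days need none.

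This matters because Section 2.2 reports a large food effect in Study 101: Cmax down 75%, AUC down 61%, and Tmax delayed from 1.5 to 6 hours in females. The 0.1 mg arm has least room to lose exposure, since Section 4.3 notes less gastric-emptying effect at 0.05 mg. At stake are the weekly ANMS GCSI-DD secondary endpoints, which depend on exposure through each treatment week, and the plasma concentrations, which are listed among the primary endpoints. With about 8 patients per arm, avoidable exposure noise is worth removing.

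**Working it through.** The protocol gives no count of home doses and no expected share of fed doses, so there is no figure of its own to reproduce.

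**1. Doses at risk.** There are 28 daily doses. The Schedule of Activities marks drug administration in clinic only at Visit 3 (Day 1) and Visit 6 (Day 28), and both of those doses are fasted under Sections 4.1 and 6.1.

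28 − 2 = 26 home doses (Days 2 to 27).

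If fasting glucose is too high at Visit 6, the patient is sent home with an extra dose and returns the next day. If a Day 28 dose is then also taken at home, the count is 27.

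**2. Does another rule fast the Visit 4 dose?** Safety laboratory tests are scheduled at Visit 4 and not at Visit 5. Appendix 2 says: "All clinical laboratory tests should be done after patients have fasted for at least 8 hours". Section 8.2.3 says: "At Visit 4 and Visit 5, the ECG will be performed approximately 4 hours after" the dose. The schedule encourages taking the ECG before blood draws. A draw d hours after the dose, with an 8-hour fast before the draw, guarantees only 8 − d hours of fasting before the dose:

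- d = 4 gives 4 hours
- d = 6 gives 2 hours

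A later draw weakens the guarantee. The Day 7 dose may be partly fasted, but this is not assured, so it stays in the count.

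**3. Worst case for one dose.** The remaining AUC after food is 1 − 0.61 = 0.39. With exposure linear in dose:

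- 0.1 mg × 0.39 = 0.039 mg fasted equivalent
- 0.5 mg × 0.39 = 0.195 mg fasted equivalent

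**4. Average weekly dose exposure.** Let L be the AUC loss per fed dose, f the fraction of at-risk doses that are fed, and n the at-risk doses in a GCSI-DD week. Relative to all-fasted dosing:

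exposure = 1 − L × f × n/7

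n = 6 in week 1 (Day 1 fasted), 7 in weeks 2 and 3, and 6 in week 4 (Day 28 fasted). The documents suggest no value for f, so a range is shown. The half-effect row is an assumption, for doses taken some hours after eating.

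| Setting | f = 10% | 25% | 50% | 100% |
|---|---|---|---|---|
| Weeks 2 and 3, L = 0.61 | 0.939 | 0.848 | 0.695 | 0.390 |
| Weeks 1 and 4, L = 0.61 | 0.948 | 0.869 | 0.739 | 0.477 |
| Weeks 2 and 3, L = 0.305 | 0.970 | 0.924 | 0.848 | 0.695 |
| 0.1 mg arm, weeks 2 and 3, L = 0.61 (mg fasted) | 0.094 | 0.085 | 0.070 | 0.039 |

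The 0.1 mg arm averages below 0.05 mg fasted equivalent only if f > 0.5/0.61 = 0.82 with the full effect.

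**5. Day 28 trough.** No PK sample is scheduled between Day 1 and Day 28. Section 2.2 gives a half-life of about 24 hours, so a dose k days earlier carries weight 0.5^k in the Day 28 pre-dose sample.

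- Days 22 to 27 (k = 1 to 6) supply 1 − 0.5^6 = 0.984 of the trough. If all six were fed with the full effect, the trough would be 1 − 0.61 × 0.984 = 0.40 of the all-fasted value.
- Days 1 to 21 supply the other 0.016. If Days 2 to 21 were all fed and later doses fasted, the trough would be about 1 − 0.61 × 0.016 = 0.99 of the all-fasted value.

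The trough can therefore be distorted by fed dosing in the last week, but says almost nothing about feeding in weeks 1 to 3.

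**The case against.** The strongest reply is that this is an omission and not a conflict. Section 4.1 contains the same 30-minute rule as the other texts and adds to it; 6.1 is silent on fasting for ordinary days and does not permit fed dosing. A patient who takes the tablet before breakfast meets every version, and most probably will. That stands, and it limits the likely size of the problem. It does not remove it, because a site or patient working from 6.1 or the Synopsis never sees the added condition.

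A reader might infer that fed doses could not be identified afterwards. The documents do not support that. Visit questioning and the Section 6.4 record of regimen deviations are partial checks, and the diary form and patient instructions are not in the documents. These checks do depend on staff knowing that a fed dose is a deviation.

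A reader might also infer that efficacy would be lost or the primary comparison compromised. Neither is shown. No exposure–symptom relation is given, so lower exposure cannot be turned into a loss on the GCSI-DD. The Day 28 breath test follows a fasted dose, which partly protects it. Randomisation and blinding make a difference in feeding between arms unlikely, and the 5-fold dose ratio is unchanged if both active arms are fed equally.

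**Conclusion.** The inconsistency is real. Up to 26 home doses per patient (27 with a glucose repeat) have a fasting requirement in one section that is missing from three other statements of the same rule. The likely consequence is added exposure variability, with possible dilution of the GCSI-DD secondary endpoints and of the Day 28 trough.

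The size is unknown because the fed share is unknown. The exposure figures above are worst cases per fed share, not forecasts. They assume that the Study 101 effect, evaluated after single doses of 0.5 to 3 mg and with no meal interval stated, carries over to 0.1 mg. The comparison with 0.05 mg also assumes that Study 102 dosing was fasted, which the documents do not state. The trough figures use simple 24-hour decay and ignore any delay in absorption.

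This is a cheap improvement of low to moderate severity.

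**What to change.** Use one rule in Sections 4.1 and 6.1, both Synopsis statements and the instructions given to patients at Visits 1 to 3: take the tablet each morning fasted, before the first meal of the day and at least 30 minutes before eating. Add one field to the existing dosing diary, either fasted yes/no or time of last meal, and use it in the compliance and exposure-response summaries.

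The cost is wording in four places plus the patient instructions, and one diary field. The downside is a slight extra burden on patients and some doses recorded as deviations that would otherwise pass unnoticed.

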6.2 Preparation, Handling, Storage, and Accountability

The Investigator or designee must maintain a log to confirm appropriate temperature conditions have been maintained during transit for all study treatment received, and any discrepancies are reported and resolved before use of the study treatment. Study treatment must be stored in the original packaging between 20 to 25° C (68 to 77° F), with deviations permitted between 15 to 30°C (59 to 86° F) and protected from extreme conditions of temperature, light, and humidity.

Version 3.0 37 of 85 20 April 2022

Only patients enrolled in the study may receive study treatment, and only authorized site staff may supply or administer study treatment. All study treatments must be stored in a secure, environmentally controlled, and monitored (manual or automated) area in accordance with the labeled storage conditions with access limited to the Investigator and authorized site staff.

The Investigator, institution, or the head of the medical institution (where applicable) is responsible for study treatment accountability, reconciliation, and record maintenance (e.g., receipt, reconciliation, and final disposition records).

Further guidance and information for the final disposition of unused study treatment are provided in the Study Reference Manual.

6.3 Measures to Minimize Bias: Randomization and Blinding

Patients who have successfully completed Screening criteria (Visit 1 and Visit 2) will return for a Randomization visit (Visit 3) where the inclusion/exclusion criteria will be evaluated and patients who meet the criteria will be randomized in a 1:1:1 ratio into one of the three treatment groups, PCS12852 0.1mg, PCS12852 0.5mg or placebo via Interactive Response Technology (IRT). The planned sample size to be randomized is 24 patients. The randomization to treatment groups will be stratified by type (IG, DG), enrolling at least 2 patients of each type in each treatment group.

The list of treatment allocations will be kept in a secure location by the CRO until approval to unblind is provided for the final analysis. Access to the treatment allocations will be monitored by Regulatory Affairs/Quality Assurance; any access to the allocations prior to unblinding the study will be documented by Regulatory Affairs/Quality Assurance and included in the Clinical Study Report.

Table 4 Measures to Minimize Bias

Study using IRT	All patients will be centrally randomized using an Interactive Response Technology (IRT). Each patient will be assigned a unique number (randomization number) that encodes the patient's assignment to one of the 3 arms of the study, according to the randomization schedule using a validated computer program. Details of the procedure are described in the IRT Manual provided to all sites.
	Study treatment will be administered/dispensed at the study visits as summarized in the SoA (Table 1).
	Returned study treatment should not be re-dispensed to the patients.

Version 3.0 38 of 85 20 April 2022

Blind break (IRT)

This is a double-blind study in which patients are blinded to study treatment. The IRT will be programmed with blind-breaking instructions. In case of an emergency, the Investigator has the sole responsibility for determining if unblinding of a patient's study treatment assignment is warranted. Patient safety must always be the first consideration in making such a determination. If the Investigator decides that unblinding is warranted, the Investigator should make every effort to contact the Medical Monitor prior to unblinding a patient's study treatment assignment unless this could delay emergency treatment for the patient. If a patient's study treatment assignment is unblinded, the Sponsor must be notified within 24 hours of this occurrence. The date and reason for the unblinding must be recorded.

The Sponsor may unblind the treatment assignment for any patient with an SAE. If the SAE requires that an expedited regulatory report be sent to one or more regulatory agencies, a copy of the report, identifying the patient's treatment assignment, may be sent to Investigators in accordance with local regulations and/or Sponsor policy.

